Inclusion criteria: A diagnosis of BD type I or II that meets DSM-V diagnostic criteria given by a trained psychiatrist and no episode in the preceding 4 weeks. Age ≥ 18 years.

Exclusion criteria: Exclusion criteria will be applied to obtain a sample reflecting the general patient population. The exclusion criteria include: Previous participation in any structured psychological intervention, such as psychoeducation or cognitive remediation, mental retardation, insufficient understanding of Kinyarwanda or deafness, alcohol or drug-dependence.

Intervention groups:

The RCT: Outpatients from the two-referral hospitals in Rwanda will be invited to participate and be allocated to intervention group or control group.

Intervention-arm: Manual-structured group psychoeducation. LGP is organized in two phases. Phase 1 of the LGP psychoeducation is mandatory and entails 8 sessions of 90 minutes over the course of 8 weeks (at one session per week) and has shown effect in western countries(21–23). Phase 2 will be offered after study completion. All groups will have 6-8 participants and two health professionals to conduct the sessions; a psychiatric nurse and either a psychologist or a psychiatric resident. Patients will be offered to invite their relatives for 2-3 psychoeducation-days for relatives.

Control group: Participants in the control group will be assigned to a waiting list and receive group-psychoeducation after the active intervention groups.

The district trial: This trial compares the impact of psychoeducation given at district level by district mental health nurses with the psychoeducation conducted at referral hospital (arm 1)

Randomization:

Study participants at the hospital level who meet the inclusion criteria and sign the informed consent form will be randomized individually into either intervention-arm or waiting list through block-randomization with a ratio of 1:1.

Patients at district level will not be randomized since we are unsure of the number of patients with BD at these levels fearing that the sample size will be too small. Instead all will be offered participation.

Outcome assessments:

All outcomes will be assessed at baseline, immediately post-intervention and at the 3rd and 6th month follow-up. The outcomes are based on the most commonly used measurements for trials on psychoeducation for individuals with BD in high and middle-income countries(18,19)

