Baseline data: The Mini-International Neuropsychiatric Interview(24) will be used to confirm psychiatric diagnosis. Demographic information regarding the participants' living circumstances, past psychiatric history and mental health service use data will also be collected from interviews and patient files.

Primary outcomes: Relapse is defined as a new mood episode of mania (scores above or equal to 20 on the Young Mania Rating Scale (YMRS)(25)), hypomania (above or equal to 12 on the YMRS), or depression (above or equal to 17 on the Hamilton Depression Scale-17(HDRS-17(26)) or mixed episode (above or equal to 20 on the YMRS and 12 on the HDRS-17).

Secondary outcomes: The Clinical Global Impression (CGI-I /CGI-S) will be used for the clinicians to assess how much the participant's condition has improved. The Medication Adherence Rating scale (MARS) will be used to assess the adherence. All participants will fill in questions about self-stigma before and after the psychoeducation.

Tertiary outcomes: A seven-item questionnaire based on The theoretical framework of acceptability(27) will be used to access the acceptability of the intervention.

The Young Mania Rating Scale and The Medication Adherence Rating scale both needs to be cultural adapted and validated using a forward–backward translation, consensus conference and cognitive interviews (approx. 15).

Sample size:

In the literature on group-psychoeducation, 13 out of 18 RCT's have reduction in general psychiatric symptom severity, incidence of relapse and hospitalization as main outcomes(18). We reviewed 18 RCT's on group psychoeducation for BD before we selected a study of Colom et al. as the base of our power calculation(18,28). The incidence of relapse in the study was (92%) (55 subjects) in the control group vs. 67% (40 subjects) in the psychoeducation group. For our study a sample size of 40 patients for each arm is required to achieve a level of 80% power with a 5% level of significance, when comparing the mean change in each intervention with the control arm via a two-sample t-test. Adjusting for a drop-out rate of 20%: $40/(1-(20/100)) = 50$ participants will be needed for each group.

Finally, for a one-year period, descriptive data on all inpatients with age > 18 years, discharged from Ndera the only inpatient psychiatric hospital, will be collected from files.

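### The only between-arm test the protocol names is an unadjusted t-test on mean change; for MARS, CGI-S and self-stigma a baseline-adjusted comparison is at least as precise and costs nothing

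*Protocol*

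**What the plan says.** The Sample size paragraph starts from relapse proportions in a published trial of group psychoeducation, 92% in controls against 67% with psychoeducation. It concludes that 40 patients per arm give 80% power at the 5% level, and it describes the test as follows: "when comparing the mean change in each intervention with the control arm via a two-sample t-test". No other between-arm method for the randomised trial appears in the protocol, and this sentence names neither an outcome nor a visit.

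Under Outcome assessments, "All outcomes will be assessed at baseline, immediately post-intervention and at the 3rd and 6th month follow-up". The secondary outcomes include the two CGI scales, self-stigma questions and adherence: "The Medication Adherence Rating scale (MARS) will be used to assess the adherence". The self-stigma sentence mentions only one measurement before and one after the psychoeducation, which does not match the four-visit statement.

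Participants at the referral hospitals are randomised individually "through block-randomization with a ratio of 1:1". Controls are on a waiting list and receive psychoeducation after the active groups. The protocol does not say how that timing relates to months 3 and 6.

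**The concern.** Relapse is a threshold event and has no mean change, so a comparison of mean change can only describe an outcome measured on a scale. Among the listed secondary outcomes these are MARS, CGI-S and self-stigma. CGI-I is already a rating of change and is not affected in this form.

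For a scale with a baseline value in a randomised trial, subtracting the baseline is one way to use it, but not the efficient way. Estimating the baseline coefficient gives the same treatment contrast in expectation, a variance that is no larger, and correction for chance baseline imbalance.

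With 40 evaluable patients per arm, precision matters. The second planned publication names self-stigma and medication adherence in its title beside recurrence. If the change-score t-test is carried into the analysis, intervals for those outcomes may be wider than the same data allow.

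**Working it through.** **The plan's own figure.** The 40 per arm comes from the relapse proportions. Take 0.92 and 0.67 (mean 0.795), two-sided 5% (sidedness is assumed), 80% power, pooled variance and no continuity correction:

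n = [1.960·√(2·0.795·0.205) + 0.842·√(0.92·0.08 + 0.67·0.33)]² / 0.25² = (1.119 + 0.457)² / 0.0625 ≈ 39.7, so 40.

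Dividing by 1 − 0.20 gives 50, as stated. The t-test route cannot be reproduced, because no mean difference or SD of change is given. At 40 per arm it would imply a standardised difference in change of 0.634.

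**Variances.** Let the follow-up SD be 1, the baseline SD be k, and their correlation be r. Per patient:

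- change score: 1 + k² − 2rk
- baseline-adjusted: 1 − r²
- difference: (1 + k² − 2rk) − (1 − r²) = (k − r)², which is never negative.

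So the change score is never more precise, whatever r and k are, apart from the one degree of freedom spent on the covariate. The two tie when r = k.

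**Size.** The protocol gives neither r nor k, so all values below are assumed. Extra patients needed by the change score = (1 + k² − 2rk)/(1 − r²) − 1.

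| | r = 0.3 | r = 0.5 | r = 0.7 | r = 0.8 |
|---|---|---|---|---|
| k = 1 | 1.40/0.91: 54% | 1.00/0.75: 33% | 0.60/0.51: 18% | 0.40/0.36: 11% |
| k = 0.7 | 1.07/0.91: 18% | 0.79/0.75: 5% | 0.51/0.51: 0% | – |
| k = 0.5 | 0.95/0.91: 4% | 0.75/0.75: 0% | 0.55/0.51: 8% | – |

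**In terms of power, with equal SDs (k = 1).** Take 40 per arm and an effect for which the change-score t-test has 80% power. Baseline adjustment at one visit then has 93.5%, 89.9%, 86.0% and 84.0% power for r = 0.3, 0.5, 0.7 and 0.8. Equivalently, it needs 26, 30, 34 or 36 per arm in place of 40. These are relative comparisons. They ignore clustering within the psychoeducation groups of 6 to 8, so they are not the trial's actual power under either method.

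**The case against.** The strongest objection is that the sentence justifies a sample size and is not an analysis plan. It stands in a paragraph about relapse and does not mention MARS, CGI-S or self-stigma. Covariate adjustment of secondary outcomes is commonly left to a statistical analysis plan, which is not shown here. The mean-change wording may simply be misplaced, and correcting the mismatch with binary relapse would rewrite it. A change-score comparison in a 1:1 randomised trial is also unbiased, so this is a matter of efficiency.

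Most of that stands, and it makes the loss conditional on the test actually being used for these outcomes. It does not remove the point. This is the only method the protocol states, a better one is available, and rewriting the sentence for relapse alone would leave the scale outcomes without an efficient comparison.

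A reader might infer three stronger things that the protocol does not support:

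- **That the baseline or the repeat visits are thrown away.** A change score uses the baseline with a fixed coefficient. The sentence names no visit, so it does not show that later visits are ignored.
- **That requiring no episode in the preceding 4 weeks makes the change score especially poor.** A narrow baseline spread means k below 1, which in the table mostly shrinks the loss. The change score is noisier than ignoring baseline only when r < k/2, which is r < 0.25 at k = 0.5. The entry rule selects on mood episodes and does not evidently restrict MARS or self-stigma.
- **That a repeated-measures model with a month-6 contrast is a free gain for all three outcomes.** Self-stigma may not be measured then, and controls may already have been treated.

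**Conclusion.** The point holds conditionally. If the stated t-test on mean change is applied to MARS, CGI-S or self-stigma, it is never more precise than baseline adjustment, apart from one degree of freedom. That direction does not depend on the correlation or on the SDs.

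The size does depend on them, and it rests wholly on assumption. It is about 11% to 54% more patients with equal SDs (r from 0.8 to 0.3), and about 0% to 18% more with a baseline SD of 0.5 to 0.7 of the follow-up SD (r from 0.3 to 0.7). Quoting only the equal-SD figures would overstate what is known. This is a no-cost improvement in efficiency on secondary outcomes. It is not a bias, and it does not show that the trial is too small.

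**What to change.** - For MARS, CGI-S and self-stigma, replace the change-score t-test with a regression of the follow-up value on arm, baseline value and hospital, at a named visit.
- Reconcile the before-and-after description of self-stigma with the statement that all outcomes are assessed at four visits.
- State up to which visit the waiting-list controls remain untreated. Use a repeated-measures version over later visits only for outcomes measured then, and only for visits at which controls are still untreated.
- Deal with the analysis of binary relapse separately.

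The adjustment itself is a change of wording. It needs no new patients, visits or instruments, and costs a degree of freedom or two for baseline and hospital. The repeated-measures extension does depend on settling the self-stigma visits and the waiting-list timing first.

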Given the enormous shortage of skilled mental health professionals in Rwanda the question that emerges is whether simple interventions such as psychoeducation could potentially be decentralized from the referral hospitals and be at least as effective and acceptable as those delivered by specialist health workers at the referral hospitals.

Project aim

The overall aim of the project is to determine the effect, feasibility and acceptability of psychoeducation for patients with BD in Rwanda at district level and referral-hospital level. Moreover, the study will explore current knowledge and practice of caregiving for individuals with BD among care providers in Rwanda.

Objectives and hypothesis

Specific objective 1: To collect descriptive data on inpatients at the only inpatient neuropsychiatric hospital in Rwanda as well as to collect data on the number of patients with BD receiving outpatient care at the referral hospitals in Rwanda. This descriptive information is crucial for understanding the service provision at the referral hospitals and the accessibility to intensive mental health care in Rwanda for patients with BD.

Hypothesis 1: We hypothesise that admission data and outpatient data will demonstrate a considerable unmet need for mental health in Rwanda.

Specific objective 2: To determine the feasibility, acceptability and effect of manual-based psychoeducation for patients with BD at the two national referral and teaching hospitals in Rwanda.

Hypothesis 2: We hypothesise that the psychoeducation at the top level of mental health care for patients with BD will improve outcomes.

Specific objective 3: To determine whether the establishment of a psychoeducation program for patients with BD at district level facilitated by district nurses, will be feasible and will show the same change over time as the psychoeducation provided by staff at hospital level.

Hypothesis 3: We hypothesise that psychoeducation conducted by district mental health nurses are feasible and will have a positive effect on patient outcome.

Specific Objective 4: To explore the perceptions and experiences with the mental health

system among patients with BD as well as their relatives to obtain information that can identify different treatment practices, and their efficacy including the use of traditional healers.

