Hypothesis 4: We hypothesise that patients with BD may have sought help other places than in the health care system for reasons like accessibility, stigma and culture. Moreover, we assume that they did not receive formal and evidence-based treatment before reaching the tertiary level of the health system and that the use of psychosocial interventions was limited.

Specific Objective 5: To assess the experience, knowledge and practice of caregiving for individuals with BD among traditional and alternative healers (TAH), community health workers (CHWs) as well as the mental health nurses at the district hospital. The assessment will contribute to an understanding of the feasibility of providing treatment for patients at the district and community level.

Hypothesis 5: We hypothesise that TAH as well as religious leaders are willing to collaborate with the formal health system. Moreover, we hypothesise that the CHWs and nurses want to provide evidence-based care including psychoeducation for patients with bipolar disorder but may lack the knowledge and skills

Relevance

[figure not shown]
Facing the enormous treatment gap for mental health as well as the tremendous lack of human resources for health, there is an urgent need for evidence-based operationally well-documented innovations that are compatible with the realities at a population level in resource-constrained settings. Only a very limited number of studies in low- and middle-income countries have been conducted on severe mental disorders. This project is essentially this quest. Potential positive outcomes may be effected not just in Rwanda, but also in similar low-resource settings elsewhere. If proven successful, relevant next steps will include having the newly established research group expand its focus area to severe mental health disorders other than BD; or to conduct studies on the drug treatment of BD in low-income settings. Moreover, the project will serve to enhance local research capacity.

Study design

The study consists of a **quantitative part** and a **qualitative part**.

The quantitative part is divided into a prospective randomized controlled trial (RCT), and a district trial (Figure 1)

Figure 1: Project division

* A psychiatric nurse and either a psychologist or a psychiatric resident will conduct the psychoeducation.

** Two district mental health nurses will conduct the psychoeducation

— RCT

----The district trial

Participants

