The qualitative part consists of three substudies. Each of the three substudies and their corresponding research question is outlined in Table 1, and the methodological approaches are described in further details in the following sections.

Table 1. Qualitative part

| # | Substudy | Research question | Empirical data | Methods |
|-------------------------|----------|---|--|----------------------|
| 1 Patients | | What is the living experience of adults with bipolar disorder in Rwanda? | Semi-structured interviews (approx. 10-20) | Qualitative analysis |
| 2 Relatives | | How do relatives experience the mental health service system? What is the impact of caregiving on the caregiver and their living experience? | Semi-structured interviews (approx. 10-15) | Qualitative analysis |
| 3 Care providers | | What knowledge, experience and practice of caregiving for individuals with BD do health providers in Rwanda have? Are TAH and religious leaders willing to collaborate with the formal health system? | Focus groups (approx. 4) | Qualitative analysis |

Semi-structured qualitative interviews with patients will be conducted using the methodological framework of phenomenology to explore their personal use and experiences of mental health care in Rwanda. Patients will be recruited from the group-psychoeducation program. Patients' relatives who sign up for psychoeducation-days for relatives will be asked if they want to participate in a semi-structured qualitative interview on the burden of caregiving.

Focus groups will also be conducted with CHWs as well as mental health nurses at different district hospitals and TAH and religious leaders. The interviews will be transcribed in their full length. Data will be analysed to explore the experience, knowledge and practice of treatment provided at district- and community level for patients with Bipolar Disorder.

Ethical Approval

The research protocol and study-related documents will be presented to the Rwandan National Ethical Committee (RNEC) for approval prior to study initiation. Informed consent will be obtained from participants after oral and written information.

A “twin model PhD project”:

[figure not shown]

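### One clause of Hypothesis 4, that prior use of psychosocial interventions was limited, cannot be fairly examined for structured interventions, because the interviewed patients are selected to have had none

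*Protocol*

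**What the plan says.** Specific Objective 4 is to explore experiences with the mental health system "among patients with BD as well as their relatives to obtain information that can identify different treatment practices". It sets no restriction to patients without earlier psychological treatment. Hypothesis 4 then assumes that "they did not receive formal and evidence-based treatment before reaching the tertiary level of the health system" and, in the same sentence, that "the use of psychosocial interventions was limited".

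The section on the qualitative part plans about 10 to 20 semi-structured patient interviews (Table 1) "to explore their personal use and experiences of mental health care in Rwanda". One source of patients is given: "Patients will be recruited from the group-psychoeducation program".

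The exclusion criteria under Participants, stated once before the RCT and the district trial are separated, include "Previous participation in any structured psychological intervention, such as psychoeducation or cognitive remediation". The same paragraph gives their purpose: "Exclusion criteria will be applied to obtain a sample reflecting the general patient population".

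**The concern.** Excluding previously treated patients is reasonable for a trial of psychoeducation. The difficulty comes from reusing the trial sample for a question about earlier treatment. A person who had a structured psychological intervention at any level of care, before or after reaching a referral hospital, is screened out and so cannot be interviewed. The interviews can then yield accounts that agree with the clause or are silent on it, but no account of earlier structured treatment that would count against it.

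What is at stake is the interpretation of one qualitative finding. A statement that interviewed patients had not used structured psychological interventions would restate the eligibility rule. The protocol's remark that the exclusions serve to reflect the general patient population makes it easier to read such a statement as a description of patients with bipolar disorder in Rwanda.

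**Working it through.** The plan states no figure on this point, so there is nothing to reproduce. The check sets the relevant places side by side.

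1. **Claim.** Hypothesis 4 expects limited use of psychosocial interventions, most naturally read as use before tertiary care.
2. **Sample.** The patients come from the group-psychoeducation program. The next sentence of the protocol recruits relatives through the psychoeducation days for relatives, which are described as part of the RCT intervention arm. The natural reading is therefore the trial program. Patients on the waiting list and in the district trial fall under the same criteria.
3. **Filter.** The exclusion covers any previous structured psychological intervention, with no limit on when or at which level of care it took place.
4. **Consequence.** Whatever the true frequency, 0 of the roughly 10 to 20 interviewees can report a previous structured psychological intervention, provided that the criterion is applied as written.
5. **Other sources.**
   - Baseline data on service use describe participants who have passed the same exclusion.
   - Relatives are attached to those patients and are to be asked about the burden of caregiving.
   - Provider focus groups serve Objective 5 and do not record patients' own earlier use.
   - The inpatient file data serve Objective 1, and no item on psychosocial treatment is stated for them.

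   None of these supplies the missing accounts.
6. **What stays open.** *Psychosocial* is wider than *structured psychological*. Unstructured counselling, help from healers, and other formal treatment before tertiary care pass the filter and can be reported.

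The next calculation only illustrates what the filter removes. Let p be the share of otherwise suitable interviewees with earlier structured treatment. The protocol gives no value, so p = 5%, 10% and 30% are assumptions, and interviewees are treated as independent draws. The chance that at least one of n interviewees could give such an account is 1 − (1 − p)^n:

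| p (assumed) | n = 10 | n = 20 | With the exclusion |
|---|---|---|---|
| 5% | 1 − 0.95^10 = 0.40 | 1 − 0.95^20 = 0.64 | 0 |
| 10% | 1 − 0.90^10 = 0.65 | 1 − 0.90^20 = 0.88 | 0 |
| 30% | 1 − 0.70^10 = 0.97 | 1 − 0.70^20 = 0.999 | 0 |

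This does not treat the interviews as a prevalence survey. It shows that without the filter a contrary account could plausibly be heard even in a small sample, and that with the filter it cannot.

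**The case against.** The strongest reply is that this is a phenomenological study of lived experience. It estimates no rate, the clause is introduced as an assumption, and a purposive sample need not be representative. That stands as far as rates go. It does not remove the problem, because the protocol lists the clause under a hypothesis, and the selection rule removes in advance one kind of account that could contradict it.

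A second reply is that the protocol does not say trial participants, and elsewhere uses similar words for the existing hospital service. The wording is indeed not fully explicit, but no recruitment route outside the study is described.

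A reader might also infer more than the documents support:

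- *That Hypothesis 4 as a whole is true by construction.* It is not. The exclusion concerns structured psychological interventions only. District hospitals have psychiatric nurses and a psychologist, so eligible patients could report unstructured support that counts against the clause. The parts on help sought elsewhere and on formal treatment are not fixed by the exclusion.
- *That the psychoeducation program launched in 2014 shows the true frequency to be above zero.* It ran at a national referral hospital, so attending it is exposure after reaching tertiary care. It says nothing about use before that. The documents do not show how many patients, if any, had structured treatment at lower levels.
- *That sampling only patients who have reached care distorts the result.* The hypothesis asks what happened before arrival at tertiary care, and patients who have arrived can answer that.
- *That the planned publication on pathways to care will report the artefact as a finding.* The protocol gives only a title for it, with no data source or intended claim.

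**Conclusion.** The point holds in a narrow form. For structured psychological interventions, the evidence on one clause of Hypothesis 4 is selected toward confirming it, and no other planned source offsets this. The number of interviewees who can report such treatment is 0 by eligibility. How far that departs from the truth cannot be stated, because the documents give no frequency of earlier treatment before tertiary care. It may be small.

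The conclusion assumes that the group-psychoeducation program is the study program, that the exclusion is applied as written, and that *psychosocial interventions* includes structured ones such as psychoeducation. The protocol's background supports the last assumption, since it uses the term directly after discussing psychoeducation. The rest of Hypothesis 4 and the trial's outcomes, sample size and randomised comparison are unaffected. This is a minor point, worth correcting because the correction is cheap.

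**What to change.** At screening, before exclusions are applied, record for every patient with bipolar disorder whether there was any earlier psychosocial or psychological intervention, of what type, and whether it came before or after reaching tertiary care. Report the number and share excluded for it next to the Hypothesis 4 results. Screening must already ask about structured intervention in order to apply the criterion, so this adds one or two items to the form.

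If that is not wanted, remove the clause, or restrict it explicitly to unstructured support among patients without earlier structured intervention. The cost is a more limited conclusion.

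Taking some of the planned 10 to 20 interviews from patients screened out for this reason is optional. It would add first-hand accounts without more interviews, but would require a recruitment route outside the program.
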